Trial participants	Parents of children aged 0 to 2 months at baseline, identified by children's centre staff, self-referral, Health Visitors and parent advisory committee. Level of need is assessed by completion of a self-report mental health questionnaire (parent) and a parent-report measure of child social and emotional development. Co-parents are included in measure completion (and in parent programmes if parent is allocated to intervention condition at each level of intervention dose).
Sample size	606 participants allocated in a ratio of 5:1 (intervention:control)

Follow-up	Measures are administered during home or community based visits at four intervals; baseline and three follow-ups (2, 9 and 18 months post baseline assessment).
Primary analysis	Repeated measures analysis on ASQ:SE-2 scores, comparing treatment and control groups to investigate the effectiveness of the proportionate delivery of the IY E-SEE steps/model overall on child social and emotional wellbeing.
Key Secondary analyses	Repeated measures analysis on PHQ-9 scores, comparing treatment and control groups to investigate the effectiveness of the proportionate delivery of the IY E-SEE steps/model overall on parent depression levels

1 Introduction

This document outlines the detailed statistical analysis plan (SAP) for the E-SEE main trial and is intended to be read in conjunction with the current study protocol (v10. This SAP is written in conjunction with the International Conference on Harmonisation topic E9 (ICH E9 Expert Working Group, 1999), guidance for the content of SAPs in clinical trials (Gamble *et al.*, 2017), applicable statistical standard operating procedures (SOPs) from the University of Sheffield Clinical Trials Research Unit (CTRU) and trial documents (Protocol and Data Validation Specification). The trial is conducted in accordance with Good Clinical Practice in Clinical Trials (ICH Harmonised Tripartite Guideline, 1996) and Medicine for Human Use (Clinical Trials) Regulations (UK Statutory Instruments, 2004).

This SAP will guide the Trial Statistician during the statistical analysis of all quantitative outcomes in order to answer the objectives of the study. It excludes the health economic and process evaluations (which will be described elsewhere).

All analysis will be performed in a validated statistical software package such as R (Team, 2012).

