7.1 General Considerations

Data will be reported according to the Consolidated Standards Of Reporting Trials (CONSORT) statement for individually randomised parallel group trials (Schulz, Altman and Moher, 2010) and extension (Juszczak *et al.*, 2019).

Summaries of continuous variables will comprise the number of observations used, mean, median, standard deviation (SD), inter-quartile range (IQR), minimum and maximum as appropriate for the distribution of the data.

Summaries of categorical variables will comprise the number of observations used, and the number and percentage of observations in each category. Tables containing the results of the statistical modelling will present the overall difference between treatment groups with two-sided 95% confidence intervals (CI) and p-values. Hypothesis tests will use a two-sided 5% significance level.

Complete details of data derivations and methods for handling missing data is covered in sections 8.1 and 9.

All analyses are based on the overall score only unless otherwise stated.

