7.6 Analysis of the primary outcome

7.6.1 Primary Analysis of the primary outcome

The ASQ:SE-2 is a set of questionnaires with different versions for different age groups. Consequently, different versions will be completed at each time point. The primary analysis will use raw ASQ:SE-2 scores as the scoring is the same across treatment arms and estimates will be easier to interpret. For ASQ:SE-2 either the 2 month or the 6 month questionnaire is administered at Follow-up 1 dependent upon the developmental age of the baby. If we observe an imbalance between arms in the number receiving the 2 months and 6 months versions we will adjust the score for those receiving the 2 months version by multiplying by 1.24. We have based the adjustment on the monitoring thresholds (25 and 30 for the 2 and 6 months surveys) and referral thresholds (35 and 45 for the 2 and 6 months surveys). The adjustment is midway between those required to preserve the monitoring threshold (30/25) and the referral threshold (45/35). If participants have completed both questionnaires, we will use the 6 months version and exclude them from the potential adjustment procedure.

The overall treatment effect will be estimated using a marginal model fitted using general estimating equations to account for the repeated measures with a Gaussian family, identity link, robust standard errors and an autoregressive covariance structure of order 1 AR(1). If the model does not converge using AR (1) we will use an unstructured correlation structure. The fixed effects will be stratifying variables (baseline ASQ:SE-2 score, baseline PHQ-9 score,

site⁴ and sex of child); potential confounders (ethnicity of the primary caregiver, marital status and highest level of education and follow up time (using an indicator variable for each time point)).

- The therapist induced clustering effect will not be fitted because the offer of IY-I and IY-T is conditional on outcome at FU1 and FU2 so clustering is confounded with treatment effect leading to biased estimation of the latter.
- The repeated measurements will be accounted for using a marginal model fitted using GEE because accounting for repeated measures using a mixed model inflates the type 1 error (random intercept only model) or gives a biased estimate of the treatment effect (random intercept and slope model).

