These analysis decisions above were based on previous research (Candlish 2019) and simulation work undertaken during SAP development included in appendix B.

Descriptive statistics will be presented for ASQ:SE-2 and PHQ-9 at each time point (Appendix Table 6). Mean ASQ:SE-2 and PHQ-9 scores and 95% CIs by treatment arm will be presented in line plots. Spaghetti plots will also be used to visualise individual changes over time.

The following categories of the categorical variables will be used:

- Ethnicity of the primary caregiver: English/Welsh/Scottish/Northern Irish/British/Irish; Any other White background, Indian, Pakistani and Any Other ethnic group.
- Marital status: Married and living together; Cohabiting/living together; Other type of relationship and Not in a relationship or separated
- Highest level of education: Higher Education and Other (see Section 10.1 for details of how this will be defined).

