7.6.2 Sensitivity Analysis of the primary outcome

Further sensitivity analyses will be carried out to assess the impact of not standardising the raw scores by applying standardisation methods described in detail in section 9.1.1. A missing data sensitivity analysis will also be conducted and is described in more detail in section 8.1.1.

A per protocol analysis was considered but deemed not to be appropriate as outlined in section 7.5.2. Similarly, complier average causal effect (CACE) analysis was deemed not to be appropriate.

⁴ Blackburn with Darwen, North Yorkshire, Portsmouth and Suffolk

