	3 Random intercept and slope; exchangeable correlation, Satterthwaite SE	3.2 (biased)	0.04?	Decreases as ICC increases	200
Naïve GEE	4 Exchangeable correlation	3.46	Increases as ICC increases	0.98	200
	5 Exchangeable correlation, robust SE	3.46	0.05	0.988	500

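### The GEE tests name no small-sample variance correction or reference distribution; the excess over 5% is negligible for the primary effect but larger where the control group is small

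*SAP*

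**What the plan says.** Section 7.6.1 specifies a marginal model fitted by GEE with "a Gaussian family, identity link, robust standard errors and an autoregressive covariance structure of order 1 AR(1". It mentions neither a finite-sample correction to the robust variance nor a t or F reference.

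The same section sets the covariates: "The fixed effects will be stratifying variables (baseline ASQ:SE-2 score, baseline PHQ-9 score", site and sex of child, followed by "potential confounders (ethnicity of the primary caregiver, marital status and highest level of education and follow up time". Ethnicity has five categories, of which the last four are "Any other White background, Indian, Pakistani and Any Other ethnic group". Marital status has four and education two. The four sites are "Blackburn with Darwen, North Yorkshire, Portsmouth and Suffolk".

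Section 7.1 sets the level: "Hypothesis tests will use a two-sided 5% significance level". The summary table gives "606 participants allocated in a ratio of 5:1 (intervention:control".

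Section 7.7 applies the primary approach to PHQ-9, and section 7.8 applies it to PSoC, EQ-5D-5L and the CARE Index. Co-parents complete PHQ-9, PSoC and EQ-5D-5L at every visit (Table 1). Section 10.1 runs the subgroup interaction tests, including site, through the primary model.

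Appendix B supports the choice of model. Table A1 lists the preferred model as "5 Exchangeable correlation, robust SE", with type I error 0.05 and power 0.988 in 500 runs.

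**The concern.** The plain sandwich variance uses fitted residuals, which are too small for people with high leverage. Leverage rises when one arm is small and when the model has many covariates with sparse categories. Both apply here, because the control arm is one sixth of the sample but carries five sixths of the variance of the treatment contrast. Taking a normal reference when the variance itself is estimated from few controls adds to the problem. The result is p-values that are too small and intervals that are too narrow for the stated 5% level.

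The SAP treats this property as decisive. Section 7.6.1 turns down the random-intercept mixed model because it inflates type I error, and Table A1 puts that model at 0.08. The preferred GEE should be held to the same standard in every analysis that uses it, including those with far fewer than 101 controls.

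**Working it through.** **Inputs from the SAP.** Two-sided alpha 0.05 (7.1). N = 606 at 5:1, so 505 intervention and 101 control. Person-level parameters in 7.6.1: intercept 1 + treatment 1 + ASQ:SE-2 1 + PHQ-9 1 + site 3 + sex 1 + ethnicity 4 + marital status 3 + education 1 = 16, plus 2 time indicators.

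**Control arm's share of the variance.** (1/101) / (1/101 + 1/505) = 505/606 = 5/6.

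**Reproducing Appendix B, model 5.** Its inputs are SD 10, correlation 0.4, effect 3.46 and 76 stepped-up participants (the sum of the 13 cluster sizes). Its text states no total N, so 606 is assumed.
- Effect, if the book effect persists in those not stepped up: (2.5 + 2.5 × (1 − 76/505) + 15 × 76/505)/2 = 3.44, against 3.46 stated.
- Variance of a two-visit mean: 100 × (1 + 0.4)/2 = 70. Adjusted for a baseline measure: 70 − 100 × 0.4² = 54.
- √(1/101 + 1/505) = 0.109. Unadjusted SE = √70 × 0.109 = 0.912, and power = Φ(3.46/0.912 − 1.96) = 0.967. Adjusted SE = √54 × 0.109 = 0.801, and power = 0.991.
- Simulated with 3,000 runs per setting: power 0.989–0.993 adjusted and 0.969–0.972 unadjusted; type I error 0.051–0.056 adjusted and 0.048–0.054 unadjusted.

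The stated 0.988 and 0.05 are therefore reproduced, most closely with baseline adjustment. With 500 runs, the 95% Monte Carlo range around 0.05 is 0.05 ± 1.96 × √(0.05 × 0.95/500) = 0.031 to 0.069, so a mild excess would not have been visible.

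**Null simulation of the 7.6.1 model.** AR(1) GEE, three visits, 5:1, 16 person-level parameters, about 15% monotone dropout, normal and skewed outcomes, 6,000 runs per cell (Monte Carlo SE about 0.3 points). Category shares, correlations and dropout are assumptions. KC is Kauermann-Carroll and MD is Mancl-DeRouen. Rejection rates in %:

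| N (controls) | Uncorrected, z | KC, t | MD, t | Uncorrected, 9 parameters |
|---|---|---|---|---|
| 606 (101) | 5.5–5.9 | 5.0–5.3 | 4.6–5.0 | not run |
| 340 (57) | 6.3–6.7 | 5.5–5.7 | 4.7–5.0 | not run |
| 240 (40) | 6.7–7.0 | 5.7–5.8 | 4.6–4.8 | 5.9 |
| 180 (30) | 7.1–7.4 | 5.5–5.7 | 4.4–4.5 | 6.1 |
| 120 (20) | 8.4–8.9 | 6.0–6.3 | 4.1–4.6 | 7.8 |
| 60 (10) | 11.3–11.6 (15 parameters) | 6.0–6.2 | 2.8–3.0 | 9.3 |

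The last column uses the Table 8 footnote's covariates: intercept 1 + treatment 1 + ASQ:SE-2 1 + PHQ-9 1 + sex 1 + site 3 + baseline measure 1 = 9.

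The mean estimated variance was about 0.975 of the true variance at 606, 0.90 at 240 and 0.83–0.84 at 120. Since √0.975 = 0.987, √0.90 = 0.949 and √0.835 = 0.914, standard errors are about 1%, 5% and 9% too small.

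**Cross-checks.** Person-mean regression with an uncorrected HC0 variance gave 5.7% at 606, 6.6–7.2% at 240 and 8.5–8.7% at 120. A further check gave 5.3–5.7% at 606 and 6.6–7.5% at 120.

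**Site interaction (10.1).** Four equal sites leave about 101/4 ≈ 25 controls each. The 3-df test with an uncorrected person-mean variance rejects 7.4–7.6% at 606, and a repeat gave about 7.3–7.5%. A leverage correction (HC3) gives 5.3–5.6%.

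**The case against.** The strongest reply is that the SAP states nothing false. It says robust and stops there, it leaves the software open, and its silence does not exclude a correction. This stands: uncorrected is an inference from silence. The common m/(m − 1) factor would not rescue it, however, since the rate at 606 stays at 5.5–5.9%.

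It is also fair to say that the primary outcome is barely touched. Section 7.5.1 keeps everyone with outcome data, so a person seen at any follow-up stays in the model. A reader might infer that the primary test is materially anti-conservative. An excess of under one percentage point does not support that.

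A reader might also infer that co-parent tests are clearly inflated. The SAP gives no number of co-parents, so the size is conditional on an assumption. Nor do 16 parameters apply everywhere without question. Section 7.8 points to the primary model, but the Table 8 footnote lists a shorter set, and the excess is smaller under it.

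Finally, one might claim that Appendix B ignored baseline adjustment and attrition. That goes too far. It mentions outcomes at three time points, its power is best matched with baseline adjustment, and the Appendix C diagram, which was not available for this check, may hold the numbers used. What can be said is narrower: model 5 used an exchangeable structure and two follow-ups, while 7.6.1 uses AR(1) and three, and 500 runs cannot detect an excess of this size.

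**Conclusion.** This is a minor point and a cheap improvement. Read as written, the GEE tests run above 5% by an amount that depends on the number of controls:

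- Primary main effect at 606: about 5.3–5.9%, negligible for the primary conclusion.
- Site interaction at 606: about 7.3–7.6%, assuming equal sites and complete data.
- Co-parent outcomes: about 6–7% at 240 and 6.6–9% at 120. Both sample sizes are assumed, and the ranges span the two covariate sets and the separate checks. At 120 the range includes the 0.08 that Table A1 reports for the random-intercept model.

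The direction is consistent across the checks. The sizes depend on assumed category shares, correlations and dropout, and on reading robust as uncorrected with a normal reference.

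**What to change.** In section 7.6.1, name one leverage-corrected sandwich variance and its reference distribution for all GEE tests, including those in 7.7, 7.8 and 10.1. One workable choice is Kauermann-Carroll with a t reference for single-parameter tests and Mancl-DeRouen with an F reference for the multi-degree-of-freedom interactions. State the degrees of freedom. The two corrections are not interchangeable: Mancl-DeRouen with t falls to about 3% at 60 participants, while Kauermann-Carroll with t stays slightly above 5% in small samples. The choice therefore has to be written down before unblinding. The rest of the model stays as it is.

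Also reconcile the Table 8 footnote with section 7.8, so that it is clear whether ethnicity, marital status and education enter the secondary-outcome models and whether the baseline value of the outcome does.

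The cost is a software option and slightly wider intervals. The variance correction leaves point estimates unchanged.

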7.6.2 Sensitivity Analysis of the primary outcome

Further sensitivity analyses will be carried out to assess the impact of not standardising the raw scores by applying standardisation methods described in detail in section 9.1.1. A missing data sensitivity analysis will also be conducted and is described in more detail in section 8.1.1.

A per protocol analysis was considered but deemed not to be appropriate as outlined in section 7.5.2. Similarly, complier average causal effect (CACE) analysis was deemed not to be appropriate.

⁴ Blackburn with Darwen, North Yorkshire, Portsmouth and Suffolk

7.7 Analysis of key secondary outcomes

The impact of the intervention on PHQ scores will be investigated using the same approach as the primary analysis of the primary outcome. Descriptive statistics will be presented for PHQ-9 at each time point (Appendix Table 6). Mean PHQ-9 scores and 95% CIs by treatment arm will be presented in line plots. Spaghetti plots will also be used to visualise individual changes over time.

The IY intervention in this trial comprises three main components – the IY-I book, IY-I and IY-T programmes. All participants who meet the eligibility requirement for being stepped up to IY-I and/or IY-T are given the opportunity to do so and there is no randomisation element in the step up. As such the following secondary analysis provides a non-randomised indicative analysis of the possible impact of individual components. The impact of individual components will be investigated using ASQ:SE-2 and PHQ-9 at the relevant follow up point with those participants in the control arm who would have been eligible for IY-I or IY-T in each case used as the control group comparator.

- Comparison between intervention and control groups at FU1 will provide an indicative analysis of IY-B;
- Comparison between intervention and control for the subgroup of parents with PHQ-9 score ≥ 5 OR Child ASQ:SE-2 score \geq Monitoring Zone at FU2 will provide an indicative analysis of IY-I;
- Comparison between intervention and control in the subgroup of parents with PHQ-9 score ≥ 5 OR Child ASQ:SE-2 score \geq Monitoring Zone at FU3 will provide an indicative analysis of IY-T.

These analyses will be conducted using multiple linear regression models including the same stratification variables (baseline ASQ:SE-2 score, baseline PHQ-9 score, sex of child and recruitment site) and potential confounders (ethnicity of the primary caregiver, marital status and highest level of education) as covariates. The mean difference, 95% confidence interval and associated p-values will be presented (Appendix Table 7).

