2.2.2 Primary care-giver and co-parent secondary outcomes

Key Secondary Outcome² for primary care-giver and co-parent

- a) Depression – to establish overall effectiveness of the IY programme, using the parent/co-parent report *Patient Health Questionnaire (PHQ-9)*.

Other Secondary outcomes for primary care-giver and co-parent

- b) Carer-child attachment/interaction – measured at 18-month follow-up using parent/co-parent report *Maternal Postnatal Attachment Scale (MPAS)* and/or *Paternal Postnatal Attachment Scale (PPAS)*.
- c) Parenting skill – using parent/co-parent report *Parent Sense of Competence (PSoC)*.
- d) Health Related Quality of Life (HRQoL) – using parent/co-parent report *EQ5D5L*.
- e) Service use – using parent report CSRI.

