4.1 Sequence generation

Randomisation is at the individual level using a web-based randomisation system developed by Sheffield CTRU in collaboration with a University spin-off company (epiGenesys) and using a randomisation sequence prepared by the trial statistician. E-SEE participants are randomised in a 5:1 ratio to intervention and control arms, stratified by:

- depression scores (PHQ-9 score ≥ 5) or child social emotional wellbeing (Child ASQ:SE2 score \geq Monitoring Zone);
- sex of child;
- sex of carer;
- recruitment site (see above).

Prior to recruitment starting a test system was made available for training purposes. Any user comments or suggestions on the usability of the system are fed back to the program developer before the system is made live.

Randomisation occurs after eligibility has been established, informed consent obtained, and baseline measures collected from parents to reduce initial attrition. The allocation schedule is concealed and the intervention arm is only confirmed once eligibility and consent are confirmed by researchers. A member of the University of York research team inputs participant information to the online system to enable randomisation, with allocation results returned immediately. The University of York trial coordinator informs families of allocation to condition.

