4.2 Inclusion in the Intervention arm

If a participant is allocated to the intervention arm, they receive the IY-I Book. Following the first follow up (2 months post baseline), only participants with a Parent PHQ-9 score ≥ 5 OR Child ASQ:SE2 score \geq 'Monitoring' in the intervention arm are offered the IY-I programme. Following the second follow up (9 months post baseline) only participants with Parent PHQ-9

³ In protocol v10 the CARE Index is described as a child attachment measure and listed as a child secondary outcome. Child attachment is just one part of the Index and we will use the overall dyadic synchrony score which is a parent-child dyad measure.

score ≥ 5 OR Child ASQ:SE2 score \geq 'Monitoring' in the intervention arm are offered the IY-T programme.

Non-research participants may be included in the IY-I and IY-T groups. Parents can be invited by service staff to join the group based on professional judgement/assessment that they meet the same eligibility criteria as research participants. We do not collect data for these participants; they attend as they would for any other parenting intervention delivered at that site. This is accepted practice in these types of research interventions when there are concerns about group size.

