7.3 Baseline Characteristics

The baseline demographics and clinical characteristics of the participants will be reported. For the continuous variables (e.g. age) mean and SD, median and IQR and minimum and maximum values will be presented. The number of observations used in each calculation will be presented alongside the summaries. For the categorical variables, (e.g. ethnicity), the number and percentage of participants in each of the categories and the total number of observations will be presented.

All baseline summaries will be presented and reported for each treatment group and in total. No statistical significance testing will be done to test baseline imbalances between the intervention arms but any noteworthy differences will be descriptively reported.

The following summaries will be presented:

Demographics

- Child: Age (weeks), Sex, Ethnicity
- Primary caregiver: Age, Sex, Ethnicity, Religion, Income, Marital Status, Highest qualification previously achieved
- Co-parent: Age, Sex, Ethnicity, Religion, Income, Marital Status, Highest qualification previously achieved

Outcome measures

-
- Child: ASQ:SE-2,
 - Primary caregiver: PHQ-9, PSoC, EQ5D-5L
 - Co-parent: PHQ-9, PSoC, EQ5D-5L
 - Parent-child dyad – CARE Index

Other measures

- Child: Premature, Difficulties at birth, Received immunisation
- Parent-child dyad – details of child feeding methods

Baseline summaries will be presented separately by child, primary caregiver and co-parent (Appendix Table 4, Table 5).

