This table will be repeated for Primary caregiver and co-parent PHQ-9 scores

[figure not shown]

Figure 2: Forest plot showing results from the primary analysis

[figure not shown]

Figure 3: Line plot of mean ASQ:SE-2 at each time point
This figure will be repeated for PHQ-9

Table 7: Results of the analysis of key secondary outcome 2

Outcome measure	n	Mean (SD) Intervention	n	Mean (SD) Control	n	Mean difference (95%CI)	Adjusted Mean difference (95%CI)*	p-value
ASQ:SE-2 at FU1	xx	xx.x(xx.x)	xx	xx.x(xx.x)	xx	xx.x(xx.x-xx.x)	xx.x(xx.x-xx.x)	0.xxxx
ASQ:SE-2 at FU2 in the subgroup of parents with PHQ-9 score >=5 OR Child ASQ:SE2 score>= Monitoring Zone	Xx	xx.x(xx.x)	xx	xx.x(xx.x)	xx	xx.x(xx.x-xx.x)	xx.x(xx.x-xx.x)	0.xxxx
ASQ:SE-2 at FU3 in the subgroup of parents with PHQ-9 score >=5 OR Child ASQ:SE2 score>= Monitoring Zone	xx	xx.x(xx.x)	xx	xx.x(xx.x)	xx	xx.x(xx.x-xx.x)	xx.x(xx.x-xx.x)	0.xxxx

This table will be repeated for primary care givers and co-parents (PHQ-9 scores)

iv. Analysis of secondary outcomes results

Table 8 : EQ5D-5L for primary care-givers

	n	Mean (SD) Intervention	n	Mean (SD) Control	n	Mean difference (95%CI)	Adjusted Mean difference (95%CI)*	p-value
Primary carer EQ5D-5L								
Baseline	xx	xx.x(xx.x)	xx	xx.x(xx.x)	xx	xx.x(xx.x-xx.x)		
FU1	xx	xx.x(xx.x)	xx	xx.x(xx.x)	xx	xx.x(xx.x-xx.x)	xx.x(xx.x-xx.x)	0.xxxx
FU2	xx	xx.x(xx.x)	xx	xx.x(xx.x)	xx	xx.x(xx.x-xx.x)	xx.x(xx.x-xx.x)	0.xxxx
FU3	xx	xx.x(xx.x)	xx	xx.x(xx.x)	xx	xx.x(xx.x-xx.x)	xx.x(xx.x-xx.x)	0.xxxx

*adjusted for baseline ASQ:SE-2 score, baseline PHQ-9 score, sex of child and recruitment site and baseline measure
 This table will be repeated for secondary outcome data collected at FU2 and FU2

Each Secondary outcomes will be reported in separate table showing outcome by time-point in a similar manner to table

[figure not shown]

Figure 4: Line plot showing mean secondary outcome scores

v. Subgroup analysis results

Table 9: Results of subgroup analysis

Subgroup	n	Mean (SD) Intervention	n	Mean (SD) Control	n	Mean difference (95%CI)*	p-value*
TBC	xx	xx.x(xx.x)	xx	xx.x(xx.x)	xx	xx.x(xx.x-xx.x)	0.xxxx
	xx	xx.x(xx.x)	xx	xx.x(xx.x)	xx	xx.x(xx.x-xx.x)	
	xx	xx.x(xx.x)	xx	xx.x(xx.x)	xx	xx.x(xx.x-xx.x)	
	xx	xx.x(xx.x)	xx	xx.x(xx.x)	xx	xx.x(xx.x-xx.x)	0.xxxx
	xx	xx.x(xx.x)	xx	xx.x(xx.x)	xx	xx.x(xx.x-xx.x)	
	xx	xx.x(xx.x)	xx	xx.x(xx.x)	xx	xx.x(xx.x-xx.x)	0.xxxx
	xx	xx.x(xx.x)	xx	xx.x(xx.x)	xx	xx.x(xx.x-xx.x)	
	xx	xx.x(xx.x)	xx	xx.x(xx.x)	xx	xx.x(xx.x-xx.x)	

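### Sections 7.6.1 and 7.7 never name the co-parent's own baseline PHQ-9 as a covariate for co-parent PHQ-9, and the covariate lists in 7.7 and 7.8 disagree with the Table 8 footnote

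*SAP*

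**What the plan says.** Section 2.2.2 lists depression, measured by PHQ-9, as the key secondary outcome "for primary care-giver and co-parent". Section 7.7 gives the analysis in one sentence: "The impact of the intervention on PHQ scores will be investigated using the same approach as the primary analysis of the primary outcome".

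The covariates of that primary model are in section 7.6.1: "The fixed effects will be stratifying variables (baseline ASQ:SE-2 score, baseline PHQ-9 score", followed by site, sex of child, three carer characteristics and follow-up time. For the component regressions, section 7.7 gives its own list, "including the same stratification variables (baseline ASQ:SE-2 score, baseline PHQ-9 score, sex of child and recruitment site", plus the same carer characteristics. The note below Table 7 in Appendix A extends these regressions: "This table will be repeated for primary care givers and co-parents (PHQ-9 scores".

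The co-parent's PHQ-9 is collected at baseline (Table 1 in section 6.1) and is among the baseline summaries in section 7.3: "Co-parent: PHQ-9, PSoC, EQ5D-5L".

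In Appendix A, the footnote to Table 8 (the EQ-5D-5L shell) lists baseline PHQ-9 among the adjustment terms and then adds the baseline of the outcome measure as a separate term. A note beneath it says that each secondary outcome will be tabulated in a similar way.

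**The concern.** Followed to the letter, 7.7 adjusts the co-parent's depression score for the carer's and the child's baselines and not for the co-parent's own. A respondent's own earlier score is usually the strongest single predictor of the later one. Leaving it out gives up precision that the data already in hand could supply. Randomisation was not stratified on co-parent depression, so a chance imbalance in it would also stay unadjusted.

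The second problem is discretion. One statistician could follow the lists in 7.7 and another the Table 8 footnote. They would fit different models to a key secondary outcome, and each could claim to have followed the plan.

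**Working it through.** **Whose baseline PHQ-9 is it?** Section 7.6.1 calls the score a stratifying variable. Section 4.1 stratifies on "depression scores (PHQ-9 score ≥ 5) or child social emotional wellbeing" without naming the person. Section 4.2 applies the same cut-off to step-up: "only participants with a Parent PHQ-9 score ≥ 5 OR Child ASQ:SE2 score". The summary table bases level of need on a questionnaire completed by the parent. Together these point to the primary carer. The SAP does not say that the term changes person when the co-parent is analysed.

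**Do the text and the table shells agree?**
- 7.7, overall PHQ-9 model: the primary-model covariates, with no separate term for the respondent's own baseline.
- 7.7, component regressions: an explicit list with the same gap. Table 7 marks its adjusted difference with an asterisk, but no footnote follows.
- 7.8, PSoC and EQ-5D-5L: the primary approach again, with no baseline PSoC or EQ-5D-5L named.
- Table 8 footnote: the stratification terms plus the outcome's own baseline.

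Table 8 therefore conflicts with 7.8 for EQ-5D-5L itself. If its note reaches PHQ-9, it conflicts with 7.7 too.

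**What does the omission cost?** The SAP gives no precision or power figure for co-parent PHQ-9, so there is nothing to reproduce. Inputs:
- Correlation between visits r = 0.4, from Appendix B. It is a simulation input for the primary outcome, not an estimate for co-parent PHQ-9. Range examined: 0.3 to 0.6.
- Correlation structure: AR(1), the planned working structure in 7.6.1, or exchangeable, as simulated in Appendix B.
- Correlation k between carer and co-parent scores: assumed 0, 0.1 or 0.3.
- Unit variance at each visit, and an equally weighted mean over three follow-ups as an approximation to the GEE estimate.

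Let V be the variance of the follow-up summary and c its covariance with the co-parent's own baseline. With k = 0, the variance ratio without versus with own baseline is V / (V − c²), and the standard error (SE) ratio is its square root.

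- Single follow-up: V = 1, c = 0.4. Ratio 1 / (1 − 0.16) = 1.190; SE ratio 1.091.
- Three follow-ups, AR(1): V = [3 + 2(2 × 0.4 + 0.16)] / 9 = 0.547; c = (0.4 + 0.16 + 0.064) / 3 = 0.208, so c² = 0.043. Ratio 0.547 / 0.503 = 1.086; SE ratio 1.042.
- Three follow-ups, exchangeable: V = (1 + 2 × 0.4) / 3 = 0.600; c = 0.4, so c² = 0.160. Ratio 0.600 / 0.440 = 1.364; SE ratio 1.168.

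Increase in SE when own baseline is omitted (k = 0):

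| r | Three follow-ups, AR(1) | Single follow-up | Three follow-ups, exchangeable |
|---|---|---|---|
| 0.3 | 2.0% | 4.8% | 9.7% |
| 0.4 | 4.2% | 9.1% | 16.8% |
| 0.5 | 7.8% | 15.5% | 26.5% |
| 0.6 | 13.7% | 25.0% | 40.2% |

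**Does keeping the carer's baseline make up for it?** Suppose the carer's baseline has covariance k × c with the co-parent's follow-up summary and correlation k with the co-parent's baseline. The ratio becomes (V − k²c²) / (V − c²). At r = 0.4 and k = 0.3:
- AR(1): (0.547 − 0.09 × 0.043) / 0.503 = 1.078, SE 3.8% larger.
- Exchangeable: (0.600 − 0.09 × 0.160) / 0.440 = 1.331, SE 15.4% larger.

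The carer's score recovers little.

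**The case against.** The strongest reply is that the plan is silent rather than wrong. Section 7.6.1 names the primary caregiver for ethnicity but not for baseline PHQ-9. The primary model adjusts ASQ:SE-2 for its own baseline, so using the same approach for co-parent PHQ-9 could reasonably mean the respondent's own PHQ-9. The Table 8 footnote shows an intention to adjust for own baseline, and neither it nor the note beneath it excludes PHQ-9. This stands to the extent that a reader might infer a deliberate decision to leave out the co-parent's baseline, and the SAP does not support that. What remains is that neither 7.6.1 nor 7.7 names the term, and that the label of stratifying variable points to the carer. The Table 8 footnote lists baseline PHQ-9 and the outcome's own baseline as two terms, which fits the reading that the first is a fixed stratification covariate.

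A reader might also take 17% as the expected loss. That is the exchangeable case only. Under AR(1) the figure is about 4%, and r = 0.4 was not set for this outcome.

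Nor does the gap bias the randomised comparison. The cost is precision, and unadjusted chance imbalance is largely the same cost described another way. The component regressions are in any case labelled indicative and non-randomised. Finally, the trial is powered on ASQ:SE-2 alone and the SAP gives no number of co-parents, so no statement about power is possible.

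**Conclusion.** The point holds as an underspecified and internally inconsistent covariate list for a key secondary outcome. Read literally, 7.7 omits a baseline that is already collected. The Table 8 footnote suggests that such an adjustment was intended.

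At r = 0.4 the omission enlarges the standard error by about 4% (AR(1), three follow-ups), 9% (single follow-up) or 17% (exchangeable, three follow-ups). Across r = 0.3 to 0.6 the ranges are 2% to 14%, 5% to 25% and 10% to 40%. These figures rest on assumed correlations and an equally weighted average of visits. Adding the term improves precision in every case examined, so this is a free improvement rather than the repair of a biased analysis.

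**What to change.** - In 7.7, state that the co-parent PHQ-9 models, both the GEE and the component regressions, include the co-parent's own baseline PHQ-9 in addition to the stratification variables, and say that the stratification PHQ-9 is the primary carer's.
- In 7.8, state that the PSoC and EQ-5D-5L models include the respondent's own baseline score, as the Table 8 footnote implies.
- Add to Table 7 the footnote that its asterisk calls for, matching the revised list in 7.7.

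The cost is two sentences and a footnote. The baseline data are already collected. The wording should be settled before the statistician receives unblinded data.
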